6.2.3 Simulation Procedures/Patient Positioning

Patients should be simulated in supine position. It is recommended to have the left arm raised and right arm down. Both arms down is acceptable as long as dose constraints can be met (avoiding beams through arms). Simulation scan should be obtained on expiratory breath hold.

6.2.4 Clinical Target Volume (CTV) and Planning Target Volume (PTV) Definitions

The CTV_primary will include the stomach GTV (as per PET/CT and endoscopy report) plus a 1-3 cm proximal-distal expansion along the length of the bowel structure (i.e. stomach, esophagus, or duodenum as applicable) This range is provided to allow more coverage near the GE junction (akin to esophageal expansions) but to prevent irradiating the entire stomach. Expansion may extend into esophagus and/or duodenum per tumor location. A 1-1.5 cm radial expansion is generated for CTV primary, cropped to GI luminal structure. Clinically suspicious locoregional lymph nodes as identified by EUS or imaging that are visible on 0.35 T MR may be included with a 1.0 cm expansion to CTV_node (or included in CTV_elective)). Both the CTV_primary and CTV_node must be evaluated for change and re-contoured daily at the machine if significantly changed per reviewing MD assessment. If the LN is not visible then the gross node CTV volume should not be changed.

CTV is generated with a 1-1.5 cm brush, creating a semicircle volume encompassing the proximal 1-1.5 cm of celiac SMA vessel, with the aorta at its posterior border and the anterior border demarcated by bowel or pancreas. Ideally, CTV_elective should not change if treatment imaging is acquired in the same position and phase of breathing as the simulation scan.

PTV is generated by a uniform 1 cm expansion about the CTV. Reducing PTV margins to modify OAR dose(s) is not permitted.

For daily adaptive treatments, patient should be aligned to CTV_elective. GTV is rigidly deformed and redrawn to match daily anatomy of stomach using diagnostic

imaging and prior fraction treatment plan. CTV_primary is created as above.

6.2.5 Normal Tissue Contours

Small bowel, large bowel, duodenum, kidneys, and spinal cord should be contoured. Since absolute rather than relative bowel volumes are to be tracked, it is not necessary to contour the entire large and small bowel. Only those loops within 1.5 cm superior and inferior or within 3 cm axial distance of the PTV must be contoured for daily adaptation. All bowel within 1.5 cm superior and inferior to the PTV should be contoured for initial planning. Gating boundary should be set at 5 mm.

6.2.6 Retrospective Plan Review

Deidentified DICOM datasets will be sent through encrypted transfer to Washington University for central review of contours and treatment plans. Initial radiation treatment plans will be overlaid on each daily anatomy and the change in dose to PTV and OARs will be determined.

6.3 Chemotherapy Guidelines

Chemotherapy will be given as per standard of care and should begin 2 to 4 weeks after completion of radiotherapy. Recommended total neoadjuvant chemotherapy regimens are:

- CAPOX (capecitabine/oxaliplatin)
- FOLFOX (oxaliplatin, leucovorin, and 5-FU)
- FLOT (docetaxel, oxaliplatin, leucovorin, and 5-FU)

However, the treating medical oncologist may prescribe other SOC total neoadjuvant chemotherapy regimen upon discussion with the WUSM PI. Additionally, if one regimen is not tolerated, subjects can move between regimens for a goal of 4 months of chemotherapy treatment total prior to surgery.

Patients who are unable to complete their total neoadjuvant therapy regimen may complete the chemotherapy postoperatively, at the discretion of the treating physician. Postoperative chemotherapy should start within 3 months of surgery. Patients who are medically inoperable will continue to receive chemotherapy until the entire regimen is complete.

A maximum (cumulative) delay of treatment of 4 weeks (or single delay of 3 weeks) is allowed per protocol due to factors/AEs listed in Section 7.0 (i.e., chemotherapy should be completed within a 5-month period). Cumulative delays in excess of 4 weeks, or single delays in excess of 3 weeks, will need to be discussed with the Principal Investigator in regard to proceeding to surgical resection. Such cases will need to be individualized depending on the clinical scenario. Please note that chemotherapy administration and AE assessment should be performed under the supervision of a medical oncologist. Dosing is to follow standard of care recommendations per institutional guidelines.

Interval imaging during chemotherapy, if obtained, is at the discretion of the treating physician.

6.4 Surgery

Exclusion of metastatic disease will be performed per institutional standard (exploratory laparoscopy or CT imaging).

Surgical resection is dependent on the location of the tumor. Prior to initiation of radiation and chemotherapy, tumor may be tattooed with ink (e.g. carbon black) so that the original tumor extent is identifiable post-radiation and chemotherapy. Tumors should be resected to negative margins as per frozen sections. Subtotal gastrectomy is appropriate for distal tumors, with total gastrectomy at the surgeon's discretion. Total gastrectomy or esophagogastrectomy are appropriate for proximal tumors. The spleen should be preserved when feasible. D2 nodal dissection is mandatory. Clips may be placed to identify areas of tumor adhesion or high risk for residual disease with documentation in the operative report.

Peritoneal washings should be obtained intraoperatively as part of surgical staging.

In the event of negative frozen but positive permanent margin, further treatment will be at the discretion of the treating physician.

6.5 Patient Clinical Outcomes Data

Clinical outcomes data (including but not limited to patient demographics (age, date of birth, weight, sex, height), tumor staging, treatment delivered, pathologic response, local failure and distant failure) will be recorded in OnCore. Each patient will be deidentified with a unique patient identification number. Only those individuals at the patient's respective institution will have access to the patient's personal health identifiers (e.g. name).

Endpoint	In order to be evaluable for this endpoint, a patient must
Primary	
Rate of pCR	Have received at least one fraction of radiation therapy and undergone surgical resection
Secondary	
Proportion of patients able to complete a full course of total neoadjuvant chemotherapy	Have received at least one fraction of radiation therapy

6.6 Definitions of Evaluability

Local control rate at 1 year post RT	Have received at least one fraction of
	radiation therapy and undergone at
	least one disease assessment
Rate of grade 3 or greater toxicity	Have received at least one fraction of
Rate of grade 5 of greater toxicity	
	radiation therapy
Overall survival at 1 year post RT	Have received at least one fraction of
	radiation therapy
Disease-free survival at 1 year post RT	Have received at least one fraction of
	radiation therapy and undergone at
	least one disease assessment
Exploratory	
Average percent difference in coverage of	Have received at least one fraction of
PTV by 95% isodose line	radiation therapy
Average percentage difference in dose to	Have received at least one fraction of
nearby OARs due to variation in OAR	radiation therapy
position	
Percentage of patients in each TCGA	Have completed radiation therapy and
molecular subtype after radiation and	neoadjuvant chemotherapy
chemotherapy	
Specific biomarkers	Have had specimens collected for
·	biomarkers
ctDNA	Have had specimens collected for
	biomarkers

Note that inevaluable patients will not be replaced.

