4.0 STUDY POPULATION

4.1 Inclusion Criteria

In order to participate in this study, a patient must meet all of the criteria listed in this section:

- 1. Newly diagnosed histologically or cytologically gastric adenocarcinoma. (Siewert III acceptable: the bulk of tumor should be in stomach; gastric tumors with extension to the gastroesophageal junction are permitted.) Patients with T1-3N0-2 are eligible. Patients with N3, or T4 disease are not eligible.
- 2. Known T-stage defined by EUS. Must have had CT of the chest/abdomen/pelvis with IV contrast.
- 3. Medically eligible to receive SOC chemotherapy.

- 4. At least 19 years of age.
- 5. ECOG performance status ≤ 2 (see Appendix A)
- 6. Normal bone marrow and organ function as defined below:
 - a. Absolute neutrophil count $\geq 1,500$ cells/mm³
 - b. Platelets $\geq 100,000 \text{ cells/mm}^3$
 - c. Creatinine clearance > 50 mL/min
- 7. The effects of the various chemotherapy agents used in this study on the developing human fetus are unknown. For this reason, women of childbearing potential and men must agree to use adequate contraception (hormonal or barrier method of birth control, abstinence) prior to study entry and for the duration of study participation. Should a woman become pregnant or suspect she is pregnant while participating in this study, she must inform her treating physician immediately. Men treated or enrolled on this protocol must also agree to use adequate contraception prior to the study, for the duration of the study, and one month after completion of the study
- 8. Ability to understand and willingness to sign an IRB approved written informed consent document (or that of legally authorized representative, if applicable).

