6.10 Duration of Follow-up

Patients will be followed for local recurrence, distant recurrence, and toxicity for 12 months after surgery (or date of definitive end of treatment for patients who do not have surgery). Follow-up visits will be include the following:

- 3-month follow-up: H&P, ECOG PS.
- 6-month follow-up: CT C/A/P, blood for ctDNA.
- 12-month follow-up: CT C/A/P

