11.0 MEASUREMENT OF EFFECT

Effect will be measured by the rate of pCR (primary and nodal) found at the time of surgical resection. Partial pathologic response will be defined as < 10% viable tumor remaining. Residual disease will be documented in the form of % treatment response and % viable tumor. No radiographic response to treatment will be recorded or assessed.

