14.3 Analysis of Secondary Endpoints

Secondary endpoints include the following:

- The proportion of patients that can complete total neoadjuvant chemotherapy.
- The local control rate at 1 year will be described as percent with 95% confidence interval. Local control is defined as no local recurrence, calculated from RT start.
- The rate of grade 3 or higher toxicity will also be described as percent with 95% confidence interval.
- Kaplan-Meier estimates will be used to describe disease-free survival (no cancer evident or death) and overall survival (survival from start of RT) at 1 year.

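### Section 6.6 requires an undefined disease assessment for 1-year DFS but not for OS; if this means a post-baseline assessment, deaths before it drop out of DFS and bias it upward

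*Combined protocol and SAP*

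**What the plan says.** The evaluability table in Section 6.6 sets different entry conditions for the two survival endpoints. The row "Overall survival at 1 year post RT" asks only for one fraction of RT. The row "Disease-free survival at 1 year post RT" asks for that fraction and, in addition, at "least one disease assessment". The local-control row carries the same addition. The section also says that inevaluable patients are not replaced.

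Section 14.3 states: "Kaplan-Meier estimates will be used to describe disease-free survival (no cancer evident or death) and overall survival". It gives the start of RT as the time origin for OS and for local control, but gives none for DFS. It does not restate the DFS population or say how a death without any assessment is handled.

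No section says what a disease assessment is. Section 11.0 concerns pathology at resection and adds: "No radiographic response to treatment will be recorded or assessed". On imaging:

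- Section 4.1, for entry: "Must have had CT of the chest/abdomen/pelvis with IV contrast".
- Section 1.0 schedules the next CT before surgery, then at the 6- and 12-month follow-up visits.
- Section 6.3, between those points: "Interval imaging during chemotherapy, if obtained, is at the discretion of the treating physician".
- Section 6.10 lists no imaging at the first follow-up visit: "3-month follow-up: H&P, ECOG PS".

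**The concern.** Death is part of the DFS endpoint, yet a patient can fail the DFS entry condition by dying. If the assessment must come after baseline, membership of the DFS set depends on surviving long enough to be assessed. The patients removed are then ones who had an event, so the error has one direction.

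DFS and OS would also rest on different denominators. Section 14.2 explains the reduced denominator for pathologic complete response (pCR) and undertakes to describe it when results are reported; nothing equivalent is written for DFS. Section 2.3.2 says clinical outcomes will be compared with historical controls, where an upward shift in DFS would flatter the regimen. The stake is limited to one descriptive secondary endpoint with no threshold or test.

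**Working it through.** **Plan's own figure.** The plan states no precision for DFS. Its only interval, 9% to 37% for a 20% pCR rate with 36 patients, reproduces as an exact interval (8.6% to 36.7% with 0.20 × 36 = 7.2 responders), but has no bearing on DFS.

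**Two readings of the clause.** If the baseline CT counts, every eligible patient already satisfies the condition, e = 0, and the DFS and OS sets coincide. If a post-baseline assessment is required, e is the number of treated patients who die before having one. Patients with interval imaging or documented progression before death stay evaluable.

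**How long a patient can go unassessed.** Inputs:

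- RT: 1 to 2 weeks (five daily fractions, up to 10 business days; Section 6.2.1).
- Gap to chemotherapy: 2 to 4 weeks (Section 6.3).
- Chemotherapy: 4 months, or 5 with permitted delays (Section 6.3), which is 17.4 to 21.7 weeks at 4.348 weeks per month.
- Surgery: 2 to 4 weeks after chemotherapy, with CT beforehand (Section 1.0).

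The earliest pre-surgery CT on the full course is 1 + 2 + 17.4 = 20.4 weeks from RT start. The latest is 2 + 4 + 21.7 + 4 = 31.7 weeks. It comes sooner for patients who go to surgery before finishing chemotherapy, which Sections 6.0 and 6.3 allow.

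**Size of the shift.** Let n be the treated patients, e the unassessed deaths and s those event-free at 1 year, with no censoring before those deaths. Kaplan-Meier then gives s/n for all treated and s/(n-e) under the clause, a ratio of n/(n-e).

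Assume n = 36 (the planned enrolment) and, as an illustration, 6 later events, so s = 30 - e:

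| e | All treated | Under the clause | Shift (points) |
|---|---|---|---|
| 0 | 30/36 = 83.3% | 30/36 = 83.3% | 0 |
| 1 | 29/36 = 80.6% | 29/35 = 82.9% | +2.3 |
| 2 | 28/36 = 77.8% | 28/34 = 82.4% | +4.6 |
| 3 | 27/36 = 75.0% | 27/33 = 81.8% | +6.8 |

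With 12 later events the shifts are +1.8 (23/36 to 23/35), +3.6 (22/36 to 22/34) and +5.3 (21/36 to 21/33).

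The exact 95% interval for 27/36 is 57.8% to 87.9%, a half-width of (87.9 - 57.8)/2 = 15.1 points. Earlier censoring changes the ratio little: at e = 3 it is 36/33 = 1.091 with none, and 34/31 = 1.097 if two patients are censored before the deaths.

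**Can DFS exceed OS?** With d later deaths and r patients alive with recurrence, OS = (n-e-d)/n and reported DFS = (n-e-d-r)/(n-e). Rearranging, DFS exceeds OS only if r < e × OS. Splitting the 6 later events as d = 4 and r = 2:

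- e = 1: OS = 31/36 = 86.1%, and 2 < 0.86 is false.
- e = 2: OS = 30/36 = 83.3%, and 2 < 1.67 is false.
- e = 3: OS = 29/36 = 80.6%, and 2 < 2.42 is true, so DFS of 81.8% exceeds OS of 80.6%.

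With d = 8 and r = 4 the inequality fails for every e up to 3, since e × OS is then below 3.

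**The case against.** The strongest reply is that only the missing definition is certain. The bias needs two further things, neither of them stated: that the assessment must be post-baseline, and that at least one treated patient dies before it. Eligibility is limited to T1-3N0-2 disease with ECOG status of 2 or better (Section 4.1). Section 2.2.3 reports no treatment-related acute grade 3 or higher toxicity in four earlier patients given this fractionation, though four patients say little. Deaths after surgery should not add to e, because a CT is scheduled beforehand. Patients operated on early are imaged earlier than 20 weeks. Since the term is undefined, a clinical examination might also count. All of this stands, and it lowers both severity and confidence.

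Section 12.0 requires monitoring reports to list the number evaluable per objective. That would reveal the smaller set but would not correct the estimate, and no section restores the excluded deaths.

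A reader might infer that the reported DFS will be inflated, or will exceed OS. The documents support neither: e is not given and may be 0, and DFS passes OS in only one of the six illustrated cases with e above 0. Nor does the early-stopping rule in Section 6.1 settle the range of e. It counts only treatment-related deaths and ends the trial only when there are more than three, so it does not cap e at 3.

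It is also fair to say that every patient has disease at entry and the plan does not explain how never-resected patients count for DFS. Matching the DFS set to the OS set leaves that separate gap open.

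**Conclusion.** The point holds in conditional form. As written, the DFS clause either does nothing (if baseline CT counts) or removes patients whose deaths are DFS events (if post-baseline is meant). The second reading is inferred, because it is the one that gives the words effect. Under it the bias can only be upward when e is above 0, provided living unassessed patients are handled the same way in both analyses. Its factor is about n/(n-e). For e = 1 to 3 with n = 36 and the assumed later events, the shift is 1.8 to 6.8 points, less than the half-width of the interval but always in the same direction.

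A reader might take this as a threat to the trial's main result. It is not: pCR, OS and toxicity have their own evaluability rows without this clause and are unaffected. This is a minor fix, held with moderate confidence.

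**What to change.** In Section 6.6, make the DFS set the same as the OS set: all patients with at least one RT fraction. In Section 14.3, state that death without a prior disease assessment is a DFS event on the date of death, state the DFS time origin, and report how many living patients have no post-baseline assessment. If the term is kept anywhere, including the local-control row, define its timing and which modalities count.

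A censoring rule for living unassessed patients, with a sensitivity analysis, is optional. With e = 3, 6 later events and one such patient among 36, the current clause gives 26/32 = 81.3%. After the fix, censoring that patient at the time origin gives 26/35 = 74.3%, taking the patient as event-free gives 27/36 = 75.0%, and as an event 26/36 = 72.2%. The choice matters by at most 2.8 points here.

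The cost is wording in two sections. No new data are needed, because deaths are already captured on the Death Form (Section 10.0). The downside is that reported DFS will be lower if such deaths occur. If the baseline CT was always meant to count, the change of analysis set and the death rule alter no result. The edit is best made before outcomes are known.

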6.7 Concomitant Therapy and Supportive Care Guidelines

Although addition of trastuzumab is not considered standard of care in the management of locally advanced gastric cancer, if the treating physician feels that adding trastuzumab would be in the patient's best interests, it will be allowed.

6.8 Women of Childbearing Potential

Women of childbearing potential (defined as women with regular menses, women with amenorrhea, women with irregular cycles, women using a contraceptive method that precludes withdrawal bleeding, and women who have had a tubal ligation) are required to have a negative pregnancy test within 21 days prior to the first dose of study treatment.

Female and male patients (along with their female partners) are required to use two forms of acceptable contraception, including one barrier method, during participation in the study and for 3 months following the last dose of study treatment.

If a patient is suspected to be pregnant, all study treatment should be immediately discontinued. In addition a positive urine test must be confirmed by a serum pregnancy test. If it is confirmed that the patient is not pregnant, the patient may resume dosing.

If a female patient or female partner of a male patient becomes pregnant during therapy or within 3 months after the last dose of study treatment, the investigator must be notified in order to facilitate outcome follow-up.

6.9 **Duration of Therapy**

If at any time the constraints of this protocol are considered to be detrimental to the patient's health and/or the patient no longer wishes to continue protocol therapy, the protocol therapy should be discontinued and the reason(s) for discontinuation documented in the case report forms.

In the absence of treatment delays due to adverse events, radiation therapy will continue for 5 fractions, neoadjuvant chemotherapy will continue for up to 4 months, and surgery will take place after that. Treatment will be discontinued if one of the following criteria applies:

- Documented and confirmed disease progression
- Death
- Adverse event(s) that, in the judgment of the investigator, may cause severe or permanent harm or which rule out continuation of study drug
- General or specific changes in the patient's condition render the patient unable to receive further treatment in the judgment of the investigator
- Suspected pregnancy
- Serious noncompliance with the study protocol
- Lost to follow-up
- Patient withdraws consent
- Investigator removes the patient from study
- The Siteman Cancer Center decides to close the study

Patients who prematurely discontinue treatment for any reason will still be followed as indicated in the study calendar.

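### Section 4.1 (item 7) accepts a single contraceptive method or abstinence, while section 6.8 requires two forms with a barrier over the same period and runs later for some early leavers

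*Combined protocol and SAP*

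**What the plan says.** **Section 4.1, item 7.** Women of childbearing potential and men "must agree to use adequate contraception (hormonal or barrier method of birth control, abstinence"). The period for both sexes is "prior to study entry and for the duration of study participation". A further sentence covers men only: their commitment runs "for the duration of the study, and one month after completion of the study". No period after the last dose is given for women.

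**Section 6.8.** Female and male patients, with the female partners of the men, are "required to use two forms of acceptable contraception, including one barrier method, during participation in the study". The full period is "during participation in the study and for 3 months following the last dose of study treatment". Abstinence does not appear. The same section sets a pregnancy-notification rule over the same interval: if a patient or a partner "becomes pregnant during therapy or within 3 months after the last dose of study treatment, the investigator must be notified".

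Neither section refers to the other.

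**The concern.** Item 7 of 4.1 is more than a check on the day of entry. The patient agrees there to a course of conduct throughout participation, which is the period 6.8 also governs. Two safety instructions therefore bind the same patient at the same time, and the one agreed to at entry is the weaker.

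Eligibility is confirmed from a signed checklist (section 5.3) and the trial is multicenter, so a site could reasonably counsel from either section. A patient counselled from 4.1 alone could use one method and depart from 6.8 without knowing it. An abstinent patient is expressly acceptable under one section and unaddressed in the other.

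For a patient who leaves soon after the last dose, 4.1 also lets the commitment lapse inside the interval in which 6.8 still wants pregnancies notified. Item 7 itself says the fetal effects of the chemotherapy agents are not known, so the instruction should be unambiguous.

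**Working it through.** The main point is a comparison of text. The end-date point needs a little arithmetic.

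**1. Same people, same time.** Both sections apply to women of childbearing potential and to men, and both cover study participation.

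**2. Each option in 4.1 held against 6.8.**
- Hormonal method alone: one form, no barrier. Does not meet 6.8.
- Barrier method alone: has the barrier, but is one form. Does not meet 6.8.
- Abstinence alone: not mentioned in 6.8, so not met as written.

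Result: 0 of 3 options, used alone, meet 6.8. In the other direction, two forms including a barrier meet 4.1 as well. Compliance with 6.8 implies compliance with 4.1, but not the reverse.

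**3. End dates.** Let d be the months from last dose to leaving the study, and treat leaving as completing the study (an assumption, needed for the men's extra month). Months of contraception after the last dose:
- 4.1, women: d
- 4.1, men: d + 1
- 6.8, both sexes: the larger of d and 3

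Section 4.1 is shorter by 3 − d for women when d is below 3, and by 3 − (d + 1) = 2 − d for men when d is below 2. At d = 0 these reach their maxima of 3 and 2 months. From d = 3 onward the two sections end together for women, and 4.1 runs one month longer for men.

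**4. Who can have d below 3?**
- Completers without postoperative chemotherapy: surgery follows chemotherapy by 2-4 weeks (0.5 to 1 month) and follow-up lasts 12 months after surgery, so d is about 12.5 to 13.
- Completers with postoperative chemotherapy: section 6.3 has it start within 3 months of surgery. As an upper bound, put a whole 5-month course after surgery: 3 + 5 = 8, so d = 12 − 8 = 4. With the 12-month visit 4 weeks (0.92 month) early, d = 11.08 − 8 = 3.08, still above 3.
- Patients without surgery: followed for 12 months from definitive end of treatment, so d is about 12.
- Patients who only stop treatment: section 6.9 keeps them in scheduled follow-up.
- Patients lost to follow-up: section 6.11 requires three missed visits. After treatment, visits fall at 3, 6 and 12 months, so three misses put d near 12. Only loss during treatment could give a small d.

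This leaves mainly patients who withdraw consent or are removed by the investigator near the last dose.

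**The case against.** The strongest reply is that 4.1 sets what a patient must accept at entry and 6.8 sets the stricter on-study rule. The two are cumulative, and following the stricter one satisfies both. Section 4.1 never says that one method is enough or that contraception may stop early, and that a site would counsel from 4.1 alone is conjecture. Most of this stands: the rules can be satisfied together, and no harm is shown. It does not remove the mismatch, because 4.1 is itself a commitment for the whole of participation, and the reply does not settle whether abstinence counts.

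On the end date, the reply is that the gap is almost empty, since a patient who has withdrawn is hard to hold to either section. That stands, and is why the point is secondary. The term study treatment is also not defined in 6.8. Chemotherapy is given as standard of care with dosing outside the protocol (section 7.2), and section 6.1 counts it as treatment only for the stopping rules. If the last dose means the last radiation fraction, the 3 months start earlier and the gap shrinks further.

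The documents do not show which standard was intended, so relaxing 6.8 would also remove the conflict. Aligning upward is proposed because 6.8 already binds patients on study.

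A reader might also infer a conflict over suspected pregnancy, because 6.9 lists it as a reason to discontinue while 6.8 says "If it is confirmed that the patient is not pregnant, the patient may resume dosing". The documents do not support that. Section 6.8 itself says "If a patient is suspected to be pregnant, all study treatment should be immediately discontinued", so both sections stop treatment on suspicion, and nothing in 6.9 forbids the specific resumption rule that 6.8 adds. Nor do the 14-day (section 4.2) and 21-day (section 6.8) pregnancy-test windows conflict; they run from different events and can both be met.

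**Conclusion.** The method mismatch holds on the text: 0 of the 3 options in 4.1, used alone, satisfy 6.8, and abstinence is left unreconciled. This is an inconsistency between two stated safety rules. It is not an impossibility, since two forms including a barrier meet both.

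The end-date difference is real but narrow: at most 3 months for women and 2 for men, and only for patients who leave the study shortly after the last dose. It assumes that leaving counts as completing the study and, for the completer figures, that chemotherapy counts as study treatment and keeps to the limits in section 6.3. Male completers face a one-month difference in the other direction.

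The documents do not say how many patients would be affected. Severity is low. The pCR endpoint, the sample size of 36 and the planned analyses are unaffected.

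**What to change.** - **Section 4.1, item 7:** replace the method and period with agreement to the 6.8 standard. That means two forms including one barrier, or complete abstinence, before study entry, during participation and through at least 3 months after the last dose of study treatment, even if the patient leaves the study.
- **Section 6.8:** state that complete abstinence satisfies the requirement.
- **Both sections:** give the same end date for men, namely the later of 3 months after the last dose and one month after study completion. Changing only one section would leave the one-month difference for male completers.

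The cost is one wording amendment, with no new tests or visits. The drawback is a stricter commitment at entry: a patient willing to use one method, but neither two methods nor abstinence, would no longer qualify. Section 6.8 already asks that patient for two forms once on study.
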